### 3.1.4. Prospective Medical Chart Data Collection

Site staff will be asked to abstract data from medical charts of patients who have completed the first patient survey. Data will be abstracted after each patient visit based on their routine care visits. Data abstracted will be recorded directly in the eCRF. A typical LN patient visits the physician every 3 months. In total there will be 5 visits ([Figure 1](#)).

- a. Visit 1: Enrolment visit
- b. Visit 2: 3-month follow-up after Visit 1
- c. Visit 3: 6-month follow-up after Visit 1
- d. Visit 4: 9-month follow-up after Visit 1
- e. Visit 5: last 12-month follow-up visit after Visit 1

We will aim for the data collection visits to be near the 3,6,9,12-month time points, however, since this is a real-world evidence study the frequencies of visits may vary from one patient to another. Therefore, we will take the closest available visit to our study time points. If a patient misses a visit, we will analyse based on available data and assume clinical status did not change. This would allow to minimise the influence of the study procedures on the typical schedule of patient and associated healthcare resource utilisation.

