#### 4.4.3. Secondary Analysis

The first secondary objective is to describe refractory LN cases, involving rituximab, and to assess changes in serological markers of disease activity (including anti-nuclear antibody, anti-dsDNA antibody and complement levels) over the treatment period. This will be achieved by first using summary statistics as per the general consideration of data analysis section at each time point. To assess one-year changes in numeric variables, the paired t-test or Wilcoxon signed rank test will be used while the McNemar's test will be used for changes in categorical variables. In addition, repeated measures analysis will be used to look at changes over the whole time period.

The second secondary objective is to assess the association between clinical factors (disease activity), biomarkers (inflammatory markers and hematological markers), treatment (type and duration of therapy) and renal remission. The variables included in the model will be taken from the measures closest to the time of enrolment. For continuous variables, the nonparametric Wilcoxon test will be used for assessing differences between the patients who attained renal remission versus patients who did not attain renal remission, while the chi-square test will be used for dichotomized variables. Statistically significant factors will be included in the multivariate logistic regression models with renal remission as the dependent variable. Odds ratio and corresponding 95% confidence intervals (CIs) will be presented.

The third secondary objective is to assess impact of LN on HRQoL over a one-year period after diagnosis or enrolment. This will be achieved by looking at changes in the SF-36 physical and mental components, and the total score at one year using the paired t-test or Wilcoxon signed rank test for non-normal distribution. Changes over all the time period will be assessed using repeated measures analysis.

The fourth secondary objective is to estimate HCRU and direct medical cost, associated with LN management across 5 Gulf countries over a one-year period. This will be carried out as per [Section 4.5. Cost Evaluation](#). Generating an estimate for the average HCRU and direct medical cost and creating the 95% CIs for those will be carried out for each country.

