The number and proportion of patients with missing data will be presented. Listwise missing will be used during data analysis. All data analyses will be done using IBM-SPSS (version 26, Armonk NY). A *p*-value of 0.05 or less will be considered statistically significant.

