#### **4.6. Data Handling Conventions**

Details about the methods of handling missing data and the analysis methods will be documented in a separate SAP.

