## 10. APPENDIX 1: DATA TABLE

Variables	Retro-spective	Enrolment* (Visit 1)	Pro-spective
Demographics			
Gender		X	
Race/ethnicity		X	
BMI		X	
Date at first SLE manifestation		X	
Date at SLE diagnosis		X	
Date at first LN manifestation		X	
Date at LN diagnosis		X	
Date at last visit in 2020		X	
Comorbidities		X	
SLE Characteristics			
SLEDAI-2K	X		X
Refractory SLE			X
Lupus Nephritis Characteristics			
LN Pathological type (Class I-V)	X		X
Active Non-Renal Clinical Manifestations of SLE			
Mucocutaneous	X		X
Central nervous system	X		X
Constitutional	X		X
Cardiopulmonary	X		X
Gastrointestinal	X		X
Hematologic	X		X
Musculoskeletal	X		X
Vasculitis	X		X
LN Clinical Manifestations			
Arthritis	X		X
Arthralgia	X		X
Photosensitisation	X		X
Skin rash	X		X
Malar rash	X		X
Neuropsychiatric disorders	X		X
Oral ulcer	X		X
Haematological abnormality	X		X
Serositis	X		X
Anti-dsDNA	X		X
Anti-U1-RNP	X		X
Anti-Sm	X		X
Anti-Rib	X		X
Anti-Scl-70	X		X
Lupus anticoagulant	X		X
Antiphospholipid	X		X
Anti-cardiolipin	X		X
C3/C4	X		X
Laboratory Tests			
White blood cell	X		X
Haemoglobin	X		X
Platelet count	X		X
Erythrocyte sedimentation rate	X		X

Variables	Retro-spective	Enrolment* (Visit 1)	Pro-spective
C-reactive protein	x		x
Serum creatinine	x		x
24-proteinuria	x		x
Urinary protein to creatinine ratio	x		x
Urine sediment	x		x
eGFR	x		x
Measured glomerular filtration rate (if eGFR is not available)	x		x
Liver function tests	x		x
Lipid profile	x		x
Plasma albumin	x		x
Renal remission	x		x
Renal Biopsy			
Activity index	x		x
Chronicity index	x		x
Number of glomeruli	x		x
Treatment			
Oral glucocorticoids	x		x
Daily dose of methylprednisolone	x		x
Daily dose of prednisolone	x		x
Antimalarial drugs	x		x
Immunosuppressants/cytotoxic	x		x
NSAIDs	x		x
Biological therapy	x		x
Quality of Life			
SF-36		x	x
Healthcare Resources/ Medical Costs			
Immunological tests			x
Haematology tests			x
Blood chemistry tests			x
Urine analysis: creatinine			x
Other fluid analysis			x
Kidney biopsy			x
Dialysis			x
Imaging tests			x
MRI			x
Computer tomography			x
Ultrasound			x
X-ray			x
Hospitalisations			x
ICU hospitalisations			x
Outpatient visits			x
Other			x

\*Enrolment or diagnosis of LN

Note: Data will be collected only if available.

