4. STATISTICAL ANALYSIS

4.1. General Considerations

For each patient in the database eligibility and proof of signing consent will be checked. Those who do not satisfy eligibility or for whom there is no proof of consent signature will not be included in the analysis.

Numeric variables will be summarised using means \pm standard deviations, medians, interquartile ranges (Q1-Q3) and, minimum and maximum values. Categorical variables will be described by frequencies and related percentages. The number of patients with missing values will be indicated for each variable.

Normality of continuous variables will be assessed using histograms and Q-Q plots.

In general, comparing numeric values between baseline and 12 months will be done using the paired t-test (or Wilcoxon signed rank test for non-normal data). Also for such variable, repeated

measures analysis will be used to test trends over time. For Dichotomous variables, the McNemar test will be used to compared between baseline and 12 months.

Significance level will be set at the 5% level. All analysis will be done using IBM-SPSS (version 27, Armonk NY).

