4.3. Handling Missing Data

Missing data in this study can arise from the retrospective part (information not in the charts), or from the prospective part where patients either refuse to answer a question or are lost to follow up. Missing data will not be imputed. The number of missing entries for each variable will be indicated.

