4.5. Specific Analyses

4.5.1. Analysis of the primary objective

Patient demographics will be summarised using the methods presented in the general consideration section (see Table 1). Similar analysis will be done for the clinical manifestations, comorbidities, severity, treatments and HRQoL of LN patients over one year (Tables 2-5).

4.5.2. Analysis of secondary objective 1

Summary statistics will be used to describe refractory LN cases and the independent t-test or Wilcoxon signed rank test along with repeated measures analysis will be used to test for changes in serological markers of disease activity at one year and over the treatment period. Changes in categorical variables at one-year period will be tested using the McNemar's test (see Table 6).

4.5.3. Analysis of secondary objective 2

Univariate and multivariate logistic regression with renal remission as the dependent variable and clinical factors and treatment as the independent variables. Odds ratios and 95% confidence intervals (CIs) will be presented. Variables with a p-value of 0.25 or less along with known associated factors with renal remission will be used to build the final multivariate model. The final multivariable model will contain only significant factors or those who have confounding effect on others in the model.(see Table 7).

4.5.4. Analysis of secondary objective 3

Changes in SF-36 total score from baseline to one year will be test for significance using the paired t-test (or Wilcoxon signed rank test for non-normal distribution. The same analysis will be done for all subscales of the SF-36 (see Table 8).

4.5.5. Analysis of secondary objective 4

For each country, the average HCRU and direct medical cost will be estimated along with its 95%CI (see Table 9).

4.5.6. Analysis of secondary objective 5

CCI

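### Listwise deletion, a ban on imputation and an unnamed five-visit repeated-measures model leave the trend tests of numeric markers open to losing every patient with one missing value

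*Protocol*

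**What the plan says.** **Trend test.** For the first secondary objective, Protocol 4.4.3 adds to the paired one-year comparison that "repeated measures analysis will be used to look at changes over the whole time period". SAP 4.1 extends this to numeric variables generally ("measures analysis will be used to test trends over time"), and SAP 4.5.2 repeats it for the serological markers. SAP Table 6 has a separate column for the repeated-measures p-value, beside visit columns for baseline and months 3, 6, 9 and 12. Neither document names the model or the software procedure.

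**Missing data.** There are three statements:
- Protocol 4.4.3: "Listwise missing will be used during data analysis".
- SAP 4.3: "Missing data will not be imputed". The SAP does not repeat the listwise rule.
- Protocol 3.1.4: "If a patient misses a visit, we will analyse based on available data and assume clinical status did not change".

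Protocol 4.6 defers to the SAP: "Details about the methods of handling missing data and the analysis methods will be documented in a separate SAP". SAP 4.3 adds only that missing entries will be counted.

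**Where the values come from.** Visits and tests follow routine care. The footnote to Protocol Appendix 1 reads "Note: Data will be collected only if available". Protocol 3.2.2 takes the laboratory result nearest each time point and gives no window. Eligibility requires renal laboratory results from the previous 12 months but no serology, and serology is what the first secondary objective tests.

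**The concern.** A classical repeated-measures ANOVA needs a value at every time point. With listwise deletion, one unordered test among five removes the patient from that marker's trend test, although the other four values were collected. Gaps are to be expected: no test is mandated, Table 6 has rows for untested and missing results, and patients lost after the third month are not replaced (Protocol 4.2).

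Three things are at stake. The trend test loses precision. If clinicians order tests according to earlier results, patients with all five values are a selected group and the trend among them is biased. And within one row of Table 6, the visit means, the paired p-value and the trend p-value can describe three different sets of patients, with no number analysed shown for either p-value.

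The rule in Protocol 3.1.4 does not settle the matter. Using available data contradicts listwise deletion. Assuming no change, if applied to a laboratory value, is a form of imputation, which SAP 4.3 excludes, and it would pull trends towards zero.

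**Working it through.** **1. The plan's own sample size.** It reproduces, but it does not concern the trend test.
- Slovin's formula: 2,240 / (1 + 2,240 × 0.067²) = 202.6.
- Logistic regression with one binary X (Protocol 3.3.2: B = 0.35, P0 = 0.200, P1 = 0.385, two-sided alpha 0.05, power 0.80). Mean response = 0.65 × 0.200 + 0.35 × 0.385 = 0.26475. Then n = [1.960 × √(0.26475 × 0.73525 / 0.35) + 0.842 × √(0.16 + 0.236775 × 0.65/0.35)]² / (0.185² × 0.65) = 200.8.

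Both agree with 200. Neither allows for dropout or missing visits, and no precision or power is stated for the repeated-measures test.

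**2. Patients complete at five visits.** Let p be the chance that a marker has a value at a given visit, and rho the within-patient correlation of being observed. The documents give neither, so both are assumed.
- Independent gaps: 200 × p⁵.
- Clustered gaps (beta-binomial): 200 × ∏ (a+i)/(a+b+i) for i = 0 to 4, with a = p(1−rho)/rho and b = (1−p)(1−rho)/rho.
- Example, p = 0.80 and rho = 0.6: a = 0.533, b = 0.133; 0.800 × 0.920 × 0.950 × 0.964 × 0.971 = 0.655, or 131 patients.

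| p | complete, rho 0 | rho 0.3 | rho 0.6 | months 0 and 12 both present (rho 0 / 0.3 / 0.6) |
|---|---|---|---|---|
| 0.95 | 155 | 171 | 181 | 181 / 183 / 186 |
| 0.90 | 118 | 146 | 163 | 162 / 167 / 173 |
| 0.80 | 66 | 104 | 131 | 128 / 138 / 147 |
| 0.70 | 34 | 72 | 103 | 98 / 111 / 123 |
| 0.60 | 16 | 48 | 79 | 72 / 86 / 101 |

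With independent gaps the complete set falls below half once p is under 0.5^(1/5) = 0.87.

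**3. Precision.** Assume baseline always present, 80% random availability at the four later visits, within-patient correlation 0.6 and SD 1. The variance of one patient's change is 2 × (1 − 0.6) = 0.8.
- Complete cases: 200 × 0.8⁴ = 82 patients; SE of the 12-month change = √(0.8/82) = 0.099.
- Paired month 0 and month 12: 200 × 0.8 = 160 patients; SE = √(0.8/160) = 0.071.
- Likelihood-based model on all observed values (simulation, unstructured covariance): SE 0.071.

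The variance ratio of complete cases to the likelihood model is (0.099/0.071)² = 1.9.

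**4. Bias.** In simulations of 200 patients with a true 12-month change of −0.30 SD, testing was made more likely after a higher earlier value, with availability of roughly 67% to 77%. Complete cases gave −0.35 to −0.38, the likelihood-based model about −0.30, and the paired comparison −0.30 to −0.31. These results depend on the assumed testing mechanism. They show the direction and possible size of the bias in the 12-month change. The power of the trend p-value was not simulated.

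**The case against.** The strongest reply is that no model is named. A mixed model on all observed values also counts as repeated-measures analysis, is available in the named software, and satisfies SAP 4.3. Protocol 4.6 makes the SAP the place for missing-data rules, and the SAP never says listwise. This stands as far as it goes: complete-case exclusion is a permitted result of the text, not a certain one. But the only deletion rule in either document is listwise, and nothing says that partial records are kept in the trend tests.

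Protocol 3.1.4 and the nearest-value rule in Protocol 3.2.2 would both retain patients. The first speaks of missed visits and clinical status, and does not clearly cover a test left unordered at an attended visit. The second helps, but without a window the same value could serve two time points, and it supplies nothing new after loss to follow-up.

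The reported 12-month change comes from the paired test, where the loss of precision and the bias largely disappear. This stands and limits the concern.

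A reader might infer that the trend results necessarily rest on a small subset and lose most of their precision. The documents give no availability figure, and the complete set runs from about 16 to about 181 of 200 across the assumptions above. A reader might also infer that every Table 6 variable is affected. The lupus anticoagulant and anticardiolipin rows show counts without p-values, and SAP 4.1 assigns McNemar's test to dichotomous variables. Testing driven by disease status is plausible but not documented.

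**Conclusion.** The concern holds for the repeated-measures trend tests of numeric markers. As written, and if a classical repeated-measures ANOVA is used, any patient missing one of five routine-care values leaves that marker's test, and the three missing-data statements cannot all be followed. At an assumed 80% availability per visit, 66 to 131 of 200 patients remain; at 90%, 118 to 163. Even in the best 90% case, 200 − 163 = 37 patients would be dropped. In the step 3 setting the variance of the 12-month change among complete cases is about twice that of a model using all values. If testing depends on earlier values, the complete-case trend is also biased.

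These sizes rest on assumed availability, clustering, correlation and testing mechanism. The descriptive primary objective is untouched and the paired one-year test is much less affected. The point should be fixed, but it does not threaten the study's main results.

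**What to change.** - In Protocol 4.4.3 and SAP 4.1, 4.3 and 4.5.2, replace listwise deletion for the numeric longitudinal markers with a likelihood-based linear mixed model. Fit visit as a categorical effect, with an unstructured within-patient covariance or a patient random effect, using all observed values without imputation.
- In Protocol 3.1.4, remove the assumption of unchanged status for these analyses, or reconcile it with the SAP.
- In SAP Table 6, print the number of patients analysed beside each p-value. The existing counts of tested, untested and missing results by visit do not give this.

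The cost is wording in two documents and slightly more analysis work, with no new data. The model relies on missingness being at random given the observed values, which should be stated as an assumption.

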#### 4.5. Cost Evaluation

Direct medical costs of LN management will be assessed per country based on laboratory analyses, medication and duration of hospitalisation during 2020.

In each country cost analysis will be determined by considerations outlined in the SAP of the study.

Direct costs will be calculated for each patient on annual basis.

The annual direct medical cost will be calculated considering resources used and unitary costs at local level, in local currencies and United States Dollars. Direct medical cost evaluation considerations are outlined in the study SAP.

To compute total cost, the direct cost components listed in [Appendix 1](#) will be summed.

Major cost drivers associated with LN management will be identified by multivariate adjusted models.

The relevance of health status, disease severity, disease activity, symptoms and organs involved, disease duration since diagnosis, number of flares endured, age/severity at disease onset, treatments used, etc as predictor variables will be established. Multiple linear regression analysis will be used to determine the best model.

Details about model specifications, parameter estimation and assumption validity will be outlined in the study SAP.

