### 3.1.6. Medical Cost / HCRU

Site staff will be asked to perform abstraction of data on HCRU from the medical charts of patients who sign the consent form and complete the first patient survey. Other data will be collected at enrolment and prospectively. These include number of laboratory tests, number of dialyses and use of imaging techniques, hospitalisations in the intensive care unit (ICU)/hospitalisations. Data abstracted will also be recorded directly in the eCRF.

Data related to the unitary cost of individual healthcare resources will be collected retrospectively at the end of prospective observation. The source of the cost information will be collected for each country separately. For each country, the payer perspective shall be taken (Ministry of Health or the tender price for the relevant payer).

The type of unitary costs will be divided for each country in laboratory tests, biopsy and imaging, medical costs, medical visits costs and hospitalisation costs. More details will be further developed in the statistical analysis plan (SAP).

The cost of illness shall be stratified by disease activity (SELDALI-2K).

The prices will be taken by the end of the year for each country/institution for each resource; if any price modification has occurred during the year, an average price will be considered for the related resource.

Inflation will not be considered since the study period is only for one year.

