### **5. LIMITATIONS**

Study limitations are as follows:

- In routine practice, limited retrospective clinical SLE/LN data are available in the participating countries. Doctors in routine practice often do not indicate SLE and LN activity scores (SELENA-SLEDAI, SLEDAI-2K) in medical documentation. Lack of data to perform the full SLE activity scales completion will not limit inclusion of patients. Investigator will capture data of SLE and LN activity scales optionally, if possible.
- HCRU and costs:
  - Relevant data will be collected in local currency, as US\$ and local currency are used based on a fixed annual rate.
  - In order to map the costs at Governmental hospitals, these hospitals will be asked to list the costs of their services and to describe consultation fees of their salaried healthcare practitioners.
  - Assumptions should also be made on out-of-pocket expenses that are not recorded.

- The participating centres will be selected based on the feasibility of providing adequate data. Given regional variations in LN risk factors and in healthcare provision (including access to specialised SLE/LN centres) within the participating countries, the data should only be extrapolated to general populations with caution.
- Since the number of patients to be recruited from each country is not prefixed, analyses by countries from where the number of patients recruited is very small will lack precision.
- Sample size of the patient population in the study may not allow to generalize the data and perform comparisons between countries and some stratified analyses. However, the data from this research will be extremely important to inform future research of lupus nephritis in larger populations.

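### The cost-driver regression has no provision for country, although each patient's cost is valued at national prices; if fitted to all patients as listed, price differences can pass for patient effects

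*Protocol*

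**What the plan says.** **How cost is built.** Protocol 3.1.6 states that "The source of the cost information will be collected for each country separately", and adds: "For each country, the payer perspective shall be taken (Ministry of Health or the tender price for the relevant payer"). Protocol 4.5 confirms this for the outcome: "The annual direct medical cost will be calculated considering resources used and unitary costs at local level, in local currencies and United States Dollars". Neither document gives a common price list or a price-level adjustment. Protocol 5 mentions a fixed annual exchange rate, which converts currency but leaves differences in tariffs and tender prices in place.

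**How cost is modelled.** Protocol 4.5 identifies major cost drivers by adjusted multivariable models, using multiple linear regression. The predictors start with "The relevance of health status, disease severity, disease activity, symptoms and organs involved" and continue with "disease duration since diagnosis, number of flares endured, age/severity at disease onset, treatments used, etc as predictor variables will be established". That makes eight groups, all of them patient, disease or treatment factors, and an open end. The adjustment set is not given. The section speaks of assessing cost by country, but does not say whether the regression is pooled or fitted country by country. It leaves model specification to the SAP.

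**What the SAP adds.** SAP 4.5.5 gives only country means of resource use and cost with 95% confidence intervals. SAP Table 9 has an all-patient cost row and country rows, but no regression. The redacted SAP 4.5.6 belongs to secondary objective 5, so it does not explain the gap.

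**Strata.** Protocol 3.1.6 also says: "The cost of illness shall be stratified by disease activity (SELDALI-2K"). No country adjustment is mentioned.

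**The concern.** A patient's cost is resource volume multiplied by the prices of that patient's country, so country enters the outcome by construction. If the regression is run on all patients with only the listed predictors, price level is an omitted variable. Any predictor whose country means happen to move with price will carry part of the price difference in its coefficient, even if it has no effect on resource use. The same applies to a cost gradient by SLEDAI-2K stratum if the strata are pooled over countries.

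Protocol 4.4.3 carries out secondary objective 4 according to section 4.5, so the driver model serves that objective, and the Protocol Summary and section 1.1 name payers among the intended audience. A payer who reads a coefficient for severity as the extra care that severe patients need would be misled if part of it is only the price list of the country where more severe patients were enrolled.

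**Working it through.** **1. Figures in the plan.** No sample size, power or effect size is stated for the cost regression, so there is no figure to reproduce. The plan's only powered model is the logistic regression for renal remission. Its N of 200 reproduces (200.8, two-sided) but does not bear on this point.

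**2. Patients per country.** 200 / 5 = 40 under an equal split, which is an assumption because Protocol 5 says: "Since the number of patients to be recruited from each country is not prefixed". Against eight predictor groups, several needing more than one parameter, and with listwise deletion (Protocol 4.4.3), five separate regressions are barely feasible. One model for all patients is the workable reading.

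**3. Mechanism.** Let cost = p_c × q, with p_c the price level of country c and q resource use (mean 1, unrelated to severity x). Let μ_c be mean severity in country c, with within-country variance 1. For equal country sizes, the slope of cost on x without country is

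slope = Cov(p_c, μ_c) / [1 + Var(μ_c)],

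taken over the five countries. It is zero if prices are equal, if mean severity is equal, or if the two are uncorrelated across countries. Price differences alone therefore create no bias.

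Example (assumed): prices 1, 1.25, 1.5, 1.75, 2 and mean severities 0, 0.25, 0.5, 0.75, 1. Both sets have deviations −0.5, −0.25, 0, 0.25, 0.5, so

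- Cov = Var(μ_c) = (0.25 + 0.0625 + 0 + 0.0625 + 0.25) / 5 = 0.125
- slope = 0.125 / 1.125 = 0.111
- divided by mean cost 1.5: 7.4% of mean cost per SD of severity, where the truth is zero.

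**4. Simulation.** All inputs are assumptions: 5 × 40 patients, gamma resource use with CV 0.71 unrelated to severity, highest-to-lowest price ratio 1.5 to 3, severity gap between extreme countries 0.5 or 1 SD, two-sided 5% test, 2,000 runs per cell. Aligned means that severity and price rise in the same country order. Random means that the severity order is unrelated to price.

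| Price ratio | Severity gap (SD) | False effect per SD, aligned (share of mean cost) | False positives, aligned | False positives, random |
|---|---|---|---|---|
| 1.5 | 0.5 | 2.3% | 7% | 5% |
| 1.5 | 1 | 4.4% | 16% | 8% |
| 2 | 0.5 | 4.1% | 12% | 7% |
| 2 | 1 | 7.4% | 31% | 11% |
| 3 | 0.5 | 6.1% | 18% | 8% |
| 3 | 1 | 11.5% | 56% | 19% |

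Repeat runs, some with log-spaced prices, put the ranges at about 6% to 58% (aligned) and 5% to 20% (random). In the random case the bias averages about zero over studies, but any one study can err in either direction. With four country indicators in the model, the mean false effect is within 0.2% of mean cost and the false-positive rate is 4% to 6%.

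**5. Precision.** With country in the model, the standard error for severity was 5% larger at price ratio 1.5 and 2% larger at ratio 2, both with a 1 SD gap.

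**The case against.** The strongest reply is that the plan has not chosen this analysis. Protocol 4.5 never says that the regression is pooled, and its by-country wording permits separate models, in which the problem does not arise. The predictor list is open, the models are called adjusted, and the details are left to the SAP. On this view the only demonstrable defect is a missing specification. All of this is right about the text: pooling is an inference, and country is unspecified, not excluded. But the SAP does not supply the model, five models of about 40 patients are hardly workable, and an open list gives no assurance that country will be included.

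Second, the aligned simulation is the worst case, and nothing in the documents says that sicker patients are in dearer countries. This also stands, which is why the random-order column is shown.

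Three stronger readings are tempting and should be resisted:

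- A reader might take the regional variation in Protocol 5 as evidence that case mix and price differ together between countries. That sentence concerns variation within the participating countries and says nothing about prices.
- A reader might infer that any factor more common in a dear country must get a positive coefficient. It depends on the covariance over all five countries.
- A reader might expect country adjustment to raise power. Step 5 shows that it can reduce precision when country is related to the predictor, and no power is planned for this model.

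On the SLEDAI-2K strata, the plan has one descriptive sentence that does not say the strata are pooled, and Protocol 5 makes activity scores optional. The concern applies there only if the strata combine countries.

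**Conclusion.** The point holds conditionally. The documents establish that the cost outcome uses country-specific prices, that country is not among the named predictors, that no price standardisation is given, and that the SAP lacks the model. If the regression is fitted to all patients on the listed predictors, price level is an uncontrolled confounder for every factor whose distribution differs between countries in a way correlated with price.

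The size cannot be known from the documents, and neither can the direction. The false-positive ranges above are illustrations: they rest on assumed price ratios, severity gaps, resource-use variation and equal country sizes. At the low end (ratio 1.5, gap 0.5 SD) the harm is slight. At ratio 3 with a 1 SD gap it is serious if aligned and still material if not. This is worth correcting before the analysis because the remedy uses data already collected. It does not show that the planned results will be wrong.

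**What to change.** In Protocol 4.5, and in a matching paragraph of SAP 4.5.5, state that the cost-driver analysis is one pooled multiple linear regression of annual direct medical cost in US dollars, with country as a fixed factor (four indicators) kept in the model whatever its p-value. Where cost by SLEDAI-2K stratum is pooled over countries, report it adjusted for country.

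An optional sensitivity analysis would revalue every patient's resource use at one common unit-price list and refit the model, so that coefficients reflect resource use alone. It is more than a rerun, because resource items from different Ministry of Health and tender sources must first be harmonised.

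The main change costs a paragraph of text, 4 degrees of freedom out of about 200, and slightly wider intervals when country is related to the predictor. No new data are needed, since country and unit prices are already collected.
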